TITLE: Clinical Effects of a New Dispatcher-Assisted Basic Life Support Training Program in a Metropolitan City: A Before-and-After Intervention Study

NCT No.: NCT02142387

Document Date: Feb. 8, 2020

Study design and setting

This was a before-and-after intervention study that took place in Seoul. The study was registered on ClinicalTrials.gov: NCT02142387. Seoul is the capital city of the Republic of Korea, with approximately 10 million people and an area of 605 km². In 2016, 4,569 OHCA occurred in Seoul and the bystander CPR rate was 29.6%.

The city has 116 ambulance stations and 24 emergency medical service (EMS) agencies with a single dispatch center operated by the Seoul Metropolitan Fire Department (SMFD). There are 149 ambulances and 1,321 emergency medical technicians (EMTs) who belong to ambulance stations. They were dispatched to 541,117 incidents in 2017. EMS ambulances are usually staffed by three personnel: one level-1 EMT (EMT-intermediated in the USA), one level-2 EMT (EMT-basic in the USA), and one trained driver. An emergency department (ED) is formally categorized into level I, level II, III, or above level by law. There are 67 EDs in Seoul: 6 level I EDs, 24 level II EDs, 36 EDs over level III, and 1 specialty center (burn care) in Seoul. The level of an ED is based on its resources, and level I and II EDs should be staffed by emergency physicians.

The SMFD started a DA-CPR program in 2010, which led to increased bystander CPR rates and survival outcomes. When primary call dispatchers detect cardiac arrest using two key questions (altered mental status and abnormal breathing), they transfer the call to a secondary call dispatcher who helps bystanders perform CPR until the ambulance arrives. All OHCA cases with dispatcher instructions are recorded in the electronic dispatcher CPR registry by the secondary call dispatchers. Dispatch medical directors, who are certified by the Ministry of Health and Welfare, are required to review about 10% of DA-CPR audio recordings and provide feedback to the dispatchers for quality assurance.

There are 25 districts in Seoul and each one has a community health center that is responsible for providing BLS training for citizens and first responders (police officers, nursing teachers, safety guards, etc.). In 2016, it was reported that 324,574 laypersons were trained by a rescue and first-aid education program including BLS.

Selections of study population

The study population included OHCA patients with presumed cardiac etiology that occurred in a private place in Seoul. They were treated by EMS providers from January 2014 to December 2017. Patients under 19 years old, those who did not receive CPR, and OHCA patients initially witnessed by EMS providers were excluded. In addition, patients with unknown survival outcomes because of a lack of medical records were also excluded.

Data source

We used the Korean OHCA registry for our data source. It is a nationwide prospective clinical registry that was established in 2006 and has been supported by the Korea Centers for Disease Control and Prevention (CDC) since 2007. Data were collected from EMS records and hospital medical records. EMS records include an EMS run sheet with information on ambulance operation, an EMS cardiac arrest registry based on Utstein-style data collection, and the dispatcher CPR registry with information on dispatcher instructions. Hospital medical records were recorded by well-trained medical record reviewers who visited all hospitals that treated OHCA patients and reviewed the medical records to extract clinical information including survival outcomes.

Interventions and control

The HEROS program is a one-hour training course that includes a 30-minute video-based self-instruction (VSI) training session, a short role-play, and a debriefing. The video consists of a bystander CPR simulation with dispatcher instructions using the trainee's own phone and practice session following demonstration by a simulated layperson. After watching the video clip, all trainees are divided into two groups and conduct a role-play as dispatchers and laypersons for 15 minutes. Finally, there is a 15-minute debriefing session with several assignments. The HEROS program focuses on cooperation with a dispatcher, from recognition of cardiac arrest to performing DA-CPR, with hands-on practice so that laypersons can provide bystander CPR immediately in a real situation. Moreover, the HEROS program emphasizes practice for providing the correct address of the scene and switching to speakerphone mode, especially for the elderly. Because dispatchers usually instruct CPR using bystanders' mobile phone, it is important for bystanders to quickly switch to speakerphone mode and place the phone on the floor. But, most elderly people are not familiar with using a mobile

phone and have difficulty switching to speakerphone mode.

Community health centers in Gangbuk, Nowon, and Junglang districts have provided the HEROS program since 2015 and were defined as the intervention group. The other 22 districts were regarded as the control group. The control group commonly used a one-hour training program that was developed by the Korea CDC and it was based on the AHA BLS provider course (http://www.cdc.go.kr/board.es?mid=a20503050000&bid=0021&tag=&act=view&list_no=127655).

The program consists of a 30-minute VSI, and a 30-minute practice debriefing session. It focuses on detailed techniques for performing high-quality chest compressions including the correct hands and body position of the bystanders. Among the four years of the study period, 2014 was the control, 2015 was the run-in period, and from 2016 to 2017 was the intervention period.

Main outcomes

The primary outcome was survival to hospital discharge. The secondary and tertiary outcomes were the return of spontaneous circulation (ROSC) and good neurological recovery (defined as a cerebral performance category of 1–2).

Statistical analysis

Counts and proportions were calculated for the categorical variables and median and interquartile ranges (IQR) were calculated for the continuous variables. A χ^2 test for the categorical variables and a Wilcoxon rank sum test or Kruskal-Wallis test for continuous variables were used to compare characteristics between the two groups. We showed the trend of survival outcomes for the intervention and control groups by year using the Cochran-Armitage test. Changes over the period in the survival outcomes between the two groups were assessed using difference-in-difference (DID) analysis. The results of the DID method are expressed as adjusted estimates and the 95% confidence interval (calculated from least-square means). All analyses were performed using SAS software, version 9.4 (SAS Institute Inc., Cary, NC, USA).

Ethical statement

This study was approved by the Institutional Review Board of Seoul National University Hospital IRB (No. 1607-210-784). Informed consent was waived and patient information was anonymized prior to analysis.

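### Does excluding patients without CPR remove the very patients the training is meant to reach?

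*Combined protocol and SAP*

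**What the plan says.** In the Combined protocol and SAP, Selections of study population takes adult, presumed-cardiac arrests in private places in Seoul and adds: "They were treated by EMS providers from January 2014 to December 2017". The next sentence gives the exclusions: "Patients under 19 years old, those who did not receive CPR, and OHCA patients initially witnessed by EMS providers were excluded". Patients whose survival outcome is unknown for lack of records are also removed. Neither treatment by EMS nor CPR is defined, and no exclusion counts are given.

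Interventions and control describes a course aimed at layperson CPR, "with hands-on practice so that laypersons can provide bystander CPR immediately in a real situation". Three districts offered it, and "The other 22 districts were regarded as the control group". Under Main outcomes, "The primary outcome was survival to hospital discharge", and "The secondary and tertiary outcomes were the return of spontaneous circulation (ROSC) and good neurological recovery". Bystander CPR is not a listed outcome. Statistical analysis compares survival changes between the two groups by difference-in-difference and also plans a comparison of characteristics, without listing the variables.

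**The concern.** The exclusion names no CPR provider, in a study whose intervention works by getting laypersons to give CPR. Read as requiring bystander CPR, the rule would select patients on a consequence of the training. A patient who would have had no CPR before HEROS and had it afterwards would enter the cohort only in the later period. The gain from a higher bystander-CPR rate would then drop out of the estimate, leaving only effects of earlier or better CPR. The cohort would also shrink sharply.

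The listed outcomes would not show which reading had been applied. The rule may also overlap with the inclusion sentence: if treatment by EMS already means resuscitation by EMS, the exclusion removes nobody, and a second analyst could not tell from the text what it did.

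**Working it through.** The plan states no sample size, effect size or exclusion count, so there is no figure of its own to reproduce. The check sets the passages side by side and then uses illustrative arithmetic.

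**1. What the wording supports**

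- The sentence just before the exclusion restricts the cohort to patients treated by EMS. A CPR rule that follows it reads most simply as a requirement that resuscitation was attempted.
- EMS-witnessed arrests are excluded separately. Those patients have little opportunity for bystander CPR, so a rule requiring bystander CPR would already remove most of them. Under the resuscitation-attempted reading, the separate exclusion has work to do.
- Where the document means layperson CPR, it says bystander CPR or DA-CPR, or names the bystander or dispatcher in the same phrase. An example is "The video consists of a bystander CPR simulation with dispatcher instructions". The exclusion has no such qualifier.
- Excluding patients without bystander CPR would discard those in whom the training is meant to act. Nothing in the document suggests that intention.

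**2. Scale of the unsupported reading**

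Study design and setting gives 4,569 arrests in Seoul in 2016 and a bystander-CPR rate of 29.6%. Arrests with bystander CPR: 4,569 × 0.296 ≈ 1,352. Arrests without: 4,569 × 0.704 ≈ 3,217. A bystander-only rule would therefore drop about 70.4% before the other criteria. These figures cover all arrests in a year inside the intervention period. They show scale and are not a study baseline.

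**3. Effect kept under each reading**

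Assumed inputs: net rise in bystander CPR in the HEROS districts from b₀ = 0.296 to b₁ = 0.396; survival s₁ = 0.10 with bystander CPR and s₀ = 0.05 without. Survival in a cohort that keeps both kinds of patient is b·s₁ + (1 − b)·s₀.

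- Before: 0.296 × 0.10 + 0.704 × 0.05 = 0.0648.
- After: 0.396 × 0.10 + 0.604 × 0.05 = 0.0698.
- Resuscitation attempted by EMS: 0.0698 − 0.0648 = +0.50 points, kept in full.
- Bystander CPR required: 0.10 − 0.10 = 0 through the CPR-rate route.

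With a rise of 5 to 15 points and s₁ of 8% to 15%, the effect kept under the attempted reading runs from 0.05 × 0.03 = 0.15 points to 0.15 × 0.10 = 1.5 points.

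**4. CPR from anyone**

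Suppose the rule keeps patients with CPR from any source. Let a share *n* have no EMS attempt, no survivors and the same bystander-CPR rate. With e the survival from step 3 (0.0648 or 0.0698), cohort survival is (1 − n)·e / [(1 − n) + n·b].

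| n | Effect in the cohort (points) | Effect on all arrests, (1 − n) × 0.50 (points) |
|---|---|---|
| 2% | 0.48 | 0.49 |
| 5% | 0.46 | 0.475 |
| 10% | 0.41 | 0.45 |

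The dilution is at most 0.04 points.

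**5. If the decision to attempt depends on bystander CPR**

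Let resuscitation be attempted with probability a₁ after bystander CPR and a₀ without, with no survivors otherwise. Survival among attempted cases is [b·a₁·s₁ + (1 − b)·a₀·s₀] / [b·a₁ + (1 − b)·a₀].

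- a₁ = 0.95, a₀ = 0.90: 0.0598/0.9148 = 6.54% before and 0.0648/0.9198 = 7.05% after, a gain of 0.51 points. On all arrests: 0.0648 − 0.0598 = 0.50 points.
- a₁ = 0.95, a₀ = 0.80: 0.05628/0.8444 = 6.67% before and 0.06178/0.8594 = 7.19% after, a gain of 0.52 points. On all arrests: 0.06178 − 0.05628 = 0.55 points.

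Even with attempt rates 15 points apart, the two effects differ by about 0.03 points.

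**The case for a change.** The best case for acting is that this criterion touches the variable the training targets, so it should leave no room for interpretation. The terms are undefined, the rule may duplicate the inclusion sentence, no exclusion counts by district group and year are promised, and the decision to attempt resuscitation follows the arrest and could depend on whether a bystander had started CPR. A defining sentence would cost almost nothing.

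Some of this stands. The text does not name the provider, and the cohort cannot be rebuilt with certainty from the wording alone. How many patients the rule removed is also unknown.

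The rest carries less weight. Overlap between an inclusion and an exclusion is harmless: if the rule removes nobody, the cohort is the same. Exclusion counts are results and belong in the patient flow of the report. The planned comparison of characteristics draws on a registry with Utstein-style data and could show the bystander-CPR share, although the variables are not listed. Dependence of the attempt on bystander CPR moved the illustrative effect very little. The large consequences belong only to the bystander-only reading, which the document does not support. Nor can a reviewer supply the definition, because only the investigators know what was applied.

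**Conclusion.** The concern identifies a real gap in wording, but one that an analyst working with this registry would fill sensibly. Read in context, the rule excludes patients in whom no resuscitation was attempted and keeps the rest whether or not a bystander gave CPR. On that reading no bias is shown and no result changes. The illustrative gain is 0.50 points, or 0.51 to 0.52 if attempts depend on bystander CPR; a CPR-from-anyone reading loses at most 0.04 points when up to 10% have no EMS attempt.

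These sizes rest on assumed survival rates, an assumed rise in bystander CPR and assumed attempt probabilities. The 29.6% is a city-wide 2016 rate for all arrests. The conclusion rests mainly on the wording around the exclusion and would reverse only if bystander CPR had in fact been required. Naming the provider and giving the counts would be good practice in the study report, but the analysis plan needs no change.

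### Do separate Cochran-Armitage trend tests in two groups of very different size mislead about the effect of the training program?

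*Combined protocol and SAP*

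**What the plan says.** The Statistical analysis section describes two analyses of survival over time, in consecutive sentences. The first is "We showed the trend of survival outcomes for the intervention and control groups by year using the Cochran-Armitage test". The second is "Changes over the period in the survival outcomes between the two groups were assessed using difference-in-difference (DID) analysis". Only the second is said to compare the groups, and only the second has a stated form of result: "The results of the DID method are expressed as adjusted estimates and the 95% confidence interval (calculated from least-square means").

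The groups and periods are set under Interventions and control. Three districts form the intervention group. For the rest, "The other 22 districts were regarded as the control group". On timing, "2014 was the control, 2015 was the run-in period, and from 2016 to 2017 was the intervention period".

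The document gives no number of analysed patients per group, no survival rate, no sample size and no significance level. It does not say that the two trend p-values will be set against each other or used as evidence of an effect. It also does not call them descriptive in so many words.

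**The concern.** The study asks whether survival changed more in the districts with the new program than elsewhere. A p-value for trend within one group does not answer that. A finding of significance in one group and not in the other is a well-known false route to a between-group claim, and it is least reliable when the groups differ greatly in size. Here the ratio of districts is 22/3 = 7.33.

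Three further features add to the unease. A test over all four years with ordinary scores counts the run-in year 2015 as one step of a linear trend. The test is unadjusted, whereas the DID is adjusted. It also treats arrests in the same district as independent.

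If a reader drew the effect of the program from the pair of trend p-values, the conclusion could be wrong, and it would mostly be wrong to the program's disadvantage, because the larger control group would usually be the one to reach significance.

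**Working it through.** The plan states no figure to reproduce. The check asks two things: how often the two trend tests disagree when the trends are the same, and whether the planned DID is misled in that case.

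**Inputs from the document**
- Districts: 3 intervention and 22 control, 25 in all.
- Arrests in Seoul in 2016: 4,569, before eligibility criteria.
- Years: 4 (2014 to 2017).

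**Assumptions**
- Half of the arrests are eligible, with patients split like districts and equal numbers each year. Intervention: 4,569 × 0.5 × 3/25 ≈ 274 per year. Control: 4,569 × 0.5 × 22/25 ≈ 2,010 per year.
- Baseline survival of 8%, the same linear trend in both groups, two-sided 5% tests, no clustering by district.

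**Formulas.** With n patients per year, slope b per year and mean survival p over the four years, the Cochran-Armitage statistic is roughly normal with mean

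δ = b × √(5n) / √(p(1 − p)),

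where 5 = 1.5² + 0.5² + 0.5² + 1.5² is the sum of squared centred year scores. Power is Φ(δ − 1.96) + Φ(−δ − 1.96). The chance that exactly one group is significant is Pc(1 − Pi) + Pi(1 − Pc), where Pc and Pi are the powers in the control and intervention groups.

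**Example, b = 0.01.** Mean survival is 0.08 + 1.5 × 0.01 = 0.095, so √(0.095 × 0.905) = 0.293.
- Control: δ = 0.01 × √10,050 / 0.293 ≈ 3.42, power 93%.
- Intervention: δ = 0.01 × √1,370 / 0.293 ≈ 1.26, power 24%.
- Exactly one significant: 0.928 × 0.757 + 0.243 × 0.072 ≈ 0.72. Of this, about 0.70 is control only and 0.02 intervention only.

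**Across slopes (8% baseline)**

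| Common trend, points/year | Control power | Intervention power | Exactly one significant |
|---|---|---|---|
| 0 | 5% | 5% | 9.5% |
| 0.25 | 15% | 6% | 19% |
| 0.5 | 43% | 10% | 44% |
| 0.75 | 74% | 16% | 66% |
| 1.0 | 93% | 24% | 72% |
| 1.5 | >99% | 45% | 55% |
| 2.0 | >99% | 66% | 34% |
| 3.0 | >99% | 92% | 8% |

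Disagreement passes 50% only between about 0.56 and 1.6 points per year. With eligible shares of 30% to 100% and baselines of 5% to 10%, the lower end of that band lies between 0.3 and 0.8 and the upper end between 0.9 and 2.3. The peak is 72% at a patient ratio of 7.33, 66% at a ratio of 5 and 75% at a ratio of 9.

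**The planned comparison.** Under a common linear trend b, each group's change from 2014 to the average of 2016 and 2017 is (2b + 3b)/2 = 2.5b. At 1 point per year that is 2.5 points in each group, so the DID is 2.5 − 2.5 = 0, whatever the group sizes. Simulation of an unadjusted DID on the risk scale with identical trends rejected in 5.0% to 5.2% of runs. The unequal sizes that make the trend p-values disagree widen the DID interval but do not bias it.

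**The case for a change.** The strongest case for a change is that nothing in the text warns a reader off comparing the p-values. The document names three outcomes, so up to six trend p-values could stand beside the DID. With only three intervention districts the DID interval may be wide, and readers may then lean on the trend tests. The contrast can even point the wrong way. With 6% baseline survival and a true trend of 1 point per year in the intervention group against 0.5 in the control group, the powers are 29% and 52%. Control-only significance then has probability 0.52 × 0.71 ≈ 37%, and intervention-only significance 0.29 × 0.48 ≈ 14%. A single model with group, year and their interaction would need no new data and would show 2015 separately.

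The arithmetic stands, and so does the advice not to contrast the p-values. The case for changing the plan does not. The harm needs a reader to use the tests for a purpose the plan gives to another method in the very next sentence. The interaction model is largely a year-by-year form of the DID already planned, and showing the within-group tests or omitting them is a matter of reporting taste. Counting 2015 as a step is acceptable in a year-by-year display. Clustering by district is a fair question, but it bears on the DID interval and should be judged there.

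**Conclusion.** No change is needed. Two within-group trend tests do not compare groups, but the plan does not ask them to. It uses them to display yearly survival and rests the comparison on an adjusted DID with a 95% confidence interval, which identical trends do not mislead.

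The chance of one significant and one non-significant trend test under identical trends ranges from about 9.5% with no trend, through a peak of about 72% near 1 point per year, to about 8% at 3 points per year. These figures rest on an assumed 50% eligible share, 8% baseline survival, patients split in the same ratio as districts (22 to 3), a linear trend, a 5% level and no clustering. The 7.33 ratio is one of districts; the document gives no patient numbers per group. The roughly 5% rejection rate of the DID is likewise for an unadjusted version without clustering.

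Analysts can reasonably report the trend tests as descriptive and draw the between-group conclusion from the DID alone, which is how the section already reads.

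### HEROS was provided in 3 of 25 districts, but no district-level variance is stated for the DID; if patients are treated as independent, the 95% CI is too narrow whenever district trends differ

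*Combined protocol and SAP*

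**What the plan says.** The Study design and setting section places training at district level: "There are 25 districts in Seoul and each one has a community health center that is responsible for providing BLS training". Interventions and control then defines exposure by district: "Community health centers in Gangbuk, Nowon, and Junglang districts have provided the HEROS program since 2015 and were defined as the intervention group", and "The other 22 districts were regarded as the control group". The periods are given as "2014 was the control, 2015 was the run-in period, and from 2016 to 2017 was the intervention period", so the contrast is one year before against two years after.

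The primary outcome is survival to hospital discharge, measured on patients. The Statistical analysis section states: "Changes over the period in the survival outcomes between the two groups were assessed using difference-in-difference (DID) analysis". On precision it adds only: "The results of the DID method are expressed as adjusted estimates and the 95% confidence interval (calculated from least-square means". SAS 9.4 is named. No regression model, covariate list, district effect, random effect, GEE, robust variance, permutation method or district-level degrees of freedom appears anywhere in the document. Nothing in that section looks redacted.

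**The concern.** The comparison has three treated units, however many patients those districts contribute. A DID removes fixed differences between districts. It does not remove changes that a district would have had between 2014 and 2016-17 without the programme, such as a local change in ambulance response, receiving hospitals or case mix. An interval built on independent patients contains only sampling error, so shared movement of patients within a district is left out.

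The conclusion on the primary outcome rests on this interval. If district trends vary, the combined drift of three districts plus sampling error can be read as a programme effect more often than the nominal 5%.

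Adding a district intercept would not help, because it removes only the constant differences that the DID already removes.

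**Working it through.** The plan gives no sample size, survival rate, intraclass correlation or interval width, so there is no figure of its own to reproduce. The check is conditional on stated assumptions.

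**Inputs from the document.** 3 treated and 22 control districts; one pre-year and two post-years. "In 2016, 4,569 OHCA occurred in Seoul", so 4,569/25 = 183 arrests per district-year before eligibility.

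**Assumed inputs.**
- Eligible share 30-60%, giving 55-110 per district-year; central case 50%, or 91. District volumes are equal.
- Survival 7%, range 4-10%.
- Drift SD *s*: an independent district shock in each period. The SD of a district's change is then √2 × *s* = 1.41*s*.

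**Step 1: sampling error only.** Treated patients: 3 × 91 = 273 before and 546 after. Control patients: 22 × 91 = 2,002 before and 4,004 after.

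SE0² = p(1−p)(1/273 + 1/546 + 1/2,002 + 1/4,004) = 0.0651 × 0.006244 = 0.000406, so SE0 = 2.02 percentage points. The patient-level half-width is 1.96 × 2.016 = 3.95 points.

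**Step 2: add district drift.** SE² = SE0² + 2*s*²(1/3 + 1/22) = 4.06 + 0.758*s*² in squared points. The three treated districts supply 0.333/0.379 = 88% of the added term, and more patients per district do not reduce it.

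**Step 3: consequences.** False-positive rate of the patient-level interval = 2[1 − Φ(1.96 × SE0/SE)]. The district-level half-width uses t on 23 df, 2.069 × SE.

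| Drift SD per period (points) | SE (points) | False-positive rate | District-level half-width (points) | Ratio to 3.95 |
|---|---|---|---|---|
| 0 | 2.02 | 5.0% | 4.17 | 1.055 |
| 1 | 2.20 | 7.2% | 4.54 | 1.15 |
| 2 | 2.66 | 13.8% | 5.51 | 1.39 |
| 3 | 3.30 | 23.1% | 6.82 | 1.73 |

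**Step 4: sensitivity, same formulas.** The false-positive rates at drift SD 1, 2 and 3 points become:
- 55-110 per district-year at 7% survival: 6.3-7.7%, 10.4-15.5% and 16.7-26.0%.
- 91 per district-year, survival 10% down to 4%: 6.6-8.8%, 11.4-19.3% and 18.8-31.7%.
- 91 and 7%, with 1, 2 and 3 points taken as the SD of the district *change*: 6.1%, 9.4% and 14.8%.

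**Step 5: simulation under no effect** (91 and 7%, constant district differences of SD 1 point, 20,000 runs per setting, 4,000-6,000 for permutation). Rejection rates at drift SD 0/1/2/3:
- patient-level z: 5.1/7.2/14.0/23.5%
- patient-level model with district intercepts: 5.0/7.0/13.7/22.7%
- uncorrected cluster-robust t: 15-18% in every setting
- equal-weight pooled t on 23 df: 5.1/5.0/4.9/5.0%
- permutation over C(25,3) = 2,300 allocations: 4.6/4.8/4.7/5.0%

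The last two depend on similar district volumes. With treated districts at half the control volume, the equal-weight t rejects 13.0/11.3/9.3/8.2%; at double volume, 1.4-3.4%. A weighted analysis on 23 df stayed at about 4-6% for volume ratios from 0.5 to 2.

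**The case against.** The strongest reply is that the plan never says patients were treated as independent. Least-square means can come from a model with district terms, so what is shown is an unstated variance method, not a wrong interval. That stands as far as it goes. But nothing stated accounts for district-level change, and the most familiar district term, an intercept, would leave the problem in place.

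A second reply is that the document gives no evidence of differing trends. It describes a divided service: "The city has 116 ambulance stations and 24 emergency medical service (EMS) agencies with a single dispatch center". It also lists 67 emergency departments of different levels. Those are static counts that mainly suggest level differences, which cancel, and the shared dispatch center and its quality review point towards common change. This is fair. The counts make some local change plausible, not demonstrated, and they say nothing of its size.

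Third, the larger drift settings are demanding. A drift SD of 3 points per period is a change SD of 4.2 points against 7% survival. The results at 2-3 points should carry less weight than the result at 1 point. None of this supports assuming zero drift.

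Finally, few events make adjustment hard. At 55-110 arrests and 7% survival, a district has about 4-8 survivors in 2014. The weighted analysis held its level with pooled or continuity-corrected variances for unadjusted changes; covariate adjustment was not tested.

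**Conclusion.** The concern holds, as a point that should be fixed. Exposure is defined on 25 districts, three of them treated, and the only stated interval for the primary outcome has no district-level component. If patients are analysed as independent, the interval is too narrow for any non-zero variation in district trends. If there is none, it is correct.

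The size cannot be taken from the documents. In the central case, true coverage of the nominal 95% interval falls from 95.0% with no drift to 92.8%, 86.2% and 76.9% at drift SD 1, 2 and 3 points per period. These figures rest on assumed eligibility, survival and drift, and on equal district volumes.

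**What to change.** State the DID model, the covariates and the variance method. Base the primary interval and p-value on the 25 district-level changes in survival (2016-17 minus 2014):

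- Regress the changes on intervention status, with weights that combine each district's sampling variance and an estimated between-district variance. Use a Knapp-Hartung t interval on 23 df.
- Because survivors per district are few, take sampling variances from pooled survival or with a continuity correction. State how covariates enter, for example through one city-wide patient-level model that supplies expected survival for each district and period.
- If district volumes prove similar, an equal-weight pooled t on 23 df would also serve. So would permutation over the 2,300 possible sets of three districts, with the interval by test inversion.
- Do not rely on a district intercept alone or an uncorrected cluster-robust standard error.
- State the assumptions. Permutation needs exchangeable districts, and the three are not said to have been chosen at random. The pooled t needs similar variances.

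The work is a re-analysis of data already held, plus wording. In the central case the interval is about 5.5% wider with no drift and about 15%, 39% and 73% wider at drift SD 1, 2 and 3 points, with a matching loss of power. If the data had already been seen, the analysis must be labelled post hoc.
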